Epilepsy surgery involves resecting epileptogenic tissues including limbic structures which may be functionally normal. Hence the emergence process can be complicated in patients having diseased limbic structures or those having therapeutic removal of limbic structures as in epilepsy surgery. Limbic structures are responsible for memory, language and executive function and hence loss of some of these higher functions is to be expected in the postoperative period. Preoperative neuropsychological assessments are often used to predict their risk for postoperative loss of higher functions and behavior changes. In our experience the investigators have seen that there is a spectrum of emergence characteristics in patients undergoing temporal lobectomy that can vary from dangerously agitated patient to much sedated, unarousable patient. Delirium and agitation can be dangerous and have serious consequences for the patient such as injury, increased pain, hemorrhage, self-extubation and removal of catheters requiring physical or chemical restraint. On the other hand, the unarousable patient may pose dangerous airway complications and limit neurological assessment in the immediate postoperative period. Hence it is essential to have a clue about post anesthesia emergence behavior in patients having epilepsy

surgeries. The aim of this study is to look at the pattern of emergence from anesthesia after epilepsy surgery and to determine if preoperative neuropsychological assessment help predict the pattern of emergence in patients undergoing anterior temporal lobectomy and amygdalohippocampectomy.

Background

Emergence from anesthesia starts with activation of deep brain structures namely subcortical and limbic regions of the brain. Later they become functionally coupled with other parts of brain including frontal and inferior parietal cortex. Arousal (spoken command) induced brain activations during emergence from anesthesia are mostly localized in deep, phylogenetically old brain structures (limbic cortex or mesial temporal structures) than in neocortex.¹

Physiologically, when emerging from deep anesthesia there will first be signs of autonomic arousal, followed by a slow return of brainstem reflexes, eventually leading to reflexive or uncoordinated movements that occur somewhat before subjects can willfully respond to simple commands. Thus, emergence of a conscious state, precedes the full recovery of neocortical processing required for establishing contact with the surroundings. The prevalence of epilepsy is around 0.4–0.8%² and 20–30% of these patients will develop medically refractory seizures²⁻⁴ and hence present for surgical treatment.

Epilepsy surgery involves resecting epileptogenic tissues including limbic structures which may be functionally normal. Anterior temporal lobectomy and amygdalohippocampectomy is a well-established surgical treatment for the patients with temporal lobe epilepsy and these parts of the brain have a role in the emergence from general anesthesia. Due to asymmetry of temporal neocortical (dominant vs nondominant) and mesial temporal functional representations, the loss of these structures and hence their functions in the postoperative period complicates emergence from anesthesia in these patients³. Preoperative neuropsychological assessments are often used to predict the risk for postoperative loss of higher functions and behavior changes.

Rationale

There are no study related interventions in this study and perioperative care of these patients will be as per our standard practice. The only study related protocol would be collecting the data on the emergence from anesthesia. The data will be collected from the time of turning off the anesthetic agents till the discharge from recovery room. Data collected include, vital signs, Glasgow coma scale (GCS), and Riker agitation- sedation score. The patients will be assessed every 5 minutes for the first 30 minutes and every 10 minutes for the next 60 minutes.

Study Objective and Hypothesis

The aim of this study was to look at the pattern of emergence from anesthesia after epilepsy surgery and to determine if preoperative neuropsychological assessment help predict the quality of emergence in patients undergoing anterior temporal lobectomy (ATL) and amygdalohippocampectomy (AH).

We hypothesized that there will be a relationship between preoperative neuropsychological assessment scores and the limbic structure (hippocampus, amygdala and thalamus) volumes with the quality of emergence from anesthesia in patients undergoing anterior temporal lobectomy and amygdalohippocampectomy.

Study Design

This prospective, observational study will be conducted after approval from institutional ethics board and written informed consent will be obtained from each subject.

Eligibility Criteria

Inclusion Criteria:

- Adult patients above the age of 18 who are scheduled for elective anterior temporal lobectomy and amygdalohippocampectomy under General Anesthesia

Exclusion Criteria:

- Lack of informed consent
- Patients needing intensive care unit postoperatively

Study Procedure

Standard perioperative management

Anesthesia and neurosurgical care of the patients is as per the standard institutional practice. Preoperatively all patients will be seen by the anesthesiologists in the pre-anesthesia consult clinic.

Intraoperatively, all patients will have standard monitoring consisting of electrocardiography (ECG), pulse oximetry, end-tidal carbon dioxide (ETCO₂), invasive and non-invasive blood pressure, temperature, urine output, depth of anesthesia (Entropy) and end tidal anesthetic agent concentration.

Anesthesia induction will be with propofol (1-2 mg/kg), fentanyl (2-3mcg/kg) and rocuronium (0.8-1.2mg/kg).

Anesthesia will be maintained with oxygen, air, sevoflurane (0.8-1 MAC (Minimal Alveolar Concentration)) and remifentanyl infusion titrated to keep entropy within 45-55.

After induction and positioning, the surgery (ATL and/or AH) will be proceeded as per standard. After dural closure, inhalational agent concentration will be decreased gradually to MAC of 0.6 and fentanyl 1-2mcg/kg administered for additional analgesia.

After the closure of scalp, inhalational agent will be turned off.

Remifentanyl infusion will be turned off once the head is disengaged from head pins and after completion of the head dressing.

The patients will be allowed to wake up with “no touch technique”.

Extubation will be done when the patients are breathing adequately, spontaneously and obeying commands.

Post-surgery, patients recovered in the post anesthesia care unit (PACU) before being discharged to the neurosurgical critical care unit.

Data Collection

Data will be collected from the time of turning off the anesthetic agents till the discharge from recovery room. Patients will be assessed every 5 minutes for the first 30 minutes and every 10 minutes for the next 60 minutes. Data collected will include patient demographics, preoperative neuropsychological assessment data, Age, Intelligence quotient (IQ), Verbal, visual, language memory, education, History of psychiatric illness, Dexterity of the patient and side of surgery, Time of emergence from anesthesia, Vital signs, Glasgow Coma Scale (GCS) score, and Riker agitation score (7-agitated;dangerous agitation, 6-very agitated, 5-agitated, 4-nonagitated;calm and cooperative, 3-sedated but arousable, 2-very sedated, 1-unarousable).

Data Analysis

There are no previous studies looking at the emergence characteristics in patients with temporal lobectomy. As this is an observational study, there are no cause effect relationship to calculate sample size. Emergence characteristics were classified as either smooth emergence (Riker scale 3-4) or agitated emergence (Riker scale >4). Correlation coefficients will be used to compare the data between preoperative neuropsychological scores and the emergence characteristics (smooth vs. agitated) and the time of emergence. Quantitative variables like hemodynamics will be analyzed using student's t-test. Qualitative variables like sex distribution will be analyzed using Chi-square test. A p-value less than 0.05 is considered significant.

CONCLUSION

Smooth emergence (wake up) from anesthesia is an important consideration in patients undergoing neurosurgical procedures as blood pressure changes associated with violent emergence can cause intracranial hemorrhage and brain swelling. At the same time, emergence should also be quick so that patients' neurological function can be assessed at a timely manner. Pattern of emergence from anesthesia is poorly investigated and understood.

REFERENCES

1. Jaakko W. Långsjo, Michael T. Alkire, et al. Returning from Oblivion: Imaging the Neural Core of Consciousness. The Journal of Neuroscience. 2012; 32:4935– 4943
3. Gilliam F. The impact of epilepsy on subjective health status. Curr Neurol Neurosci Rep 2003; 3:357–62

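### The intensive-care exclusion gives no time of assessment; it probably means care planned before surgery, but as worded it also reaches need arising during or after emergence and could then remove patients partly on the outcome

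*Combined protocol and SAP*

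**What the plan says.** All references are to the combined protocol and SAP.

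- **Eligibility Criteria.** Patients enter if they are "scheduled for elective anterior temporal lobectomy and amygdalohippocampectomy under General Anesthesia". The two exclusions are lack of consent and "Patients needing intensive care unit postoperatively". The second has no time of assessment and no definition of the unit.
- **Standard perioperative management.** Before surgery, "Preoperatively all patients will be seen by the anesthesiologists in the pre-anesthesia consult clinic". After it, "patients recovered in the post anesthesia care unit (PACU) before being discharged to the neurosurgical critical care unit". The plan describes this pathway without qualification.
- **Data Collection.** On the recording window, the plan states: "Data will be collected from the time of turning off the anesthetic agents till the discharge from recovery room". The Riker scale is recorded over its full range, including "3-sedated but arousable, 2-very sedated, 1-unarousable".
- **Data Analysis.** Riker 3-4 is classified as smooth and above 4 as agitated. Riker 1-2 has no class. Preoperative scores are to be correlated with the smooth/agitated class and with time of emergence.
- **Introductory text.** Emergence after temporal lobectomy "can vary from dangerously agitated patient to much sedated, unarousable patient". Hemorrhage and self-extubation are named among the consequences of agitation, and airway complications among the risks of the unarousable patient.

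The plan has no rule for retaining, analysing or counting patients excluded after consent.

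**The concern.** The inclusion rule and the consent exclusion describe the patient before surgery. The intensive-care exclusion describes a state after surgery. Outcome recording starts when the agents are turned off, so need that arises from then on cannot be a baseline characteristic. It may be a consequence of the emergence that the study sets out to describe.

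If such patients were excluded, both ends of the Riker scale could be thinned out. The description of emergence would look milder than it was, and the association with preoperative scores would be estimated in a group selected partly on the outcome. Nothing in the plan would bring this to light, because it does not require post-consent exclusions to be counted.

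**Working it through.** The plan states no figure on this point, so there is none to reproduce. The check is mainly a reading of the text.

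**Step 1: when could the need be judged?**

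| Time of judgement | Relation to the outcome window | Consequence |
|---|---|---|
| Before surgery (planned) | Before it | Baseline restriction; little or no bias |
| During surgery | Before agents off | Exclusion before emergence is observed; count and reasons needed |
| After agents off | Within or after it | Exclusion can depend on the outcome |

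The wording fits all three rows, and no other section narrows it.

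**Step 2: does the third row imply bias?** Only if need is more frequent after bad emergence. The introductory text names serious events at both extremes, but no section says that they lead to intensive care. That step is an inference.

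**Step 3: would such patients have usable data?** Assessments are every 5 minutes for 30 minutes and then every 10 minutes for 60 minutes: 30/5 + 60/10 = 12 at most, assuming that the clock starts at agents off and no time-zero score is taken. A patient whose series stopped at 20 minutes would still have 20/5 = 4 scores.

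**Step 4: illustration only.** Every input is assumed. Let the true shares be 20% agitated, 70% smooth and 10% Riker 1-2. Let 5% of smooth patients need intensive care, and proportions *q* of agitated and *u* of Riker 1-2 patients. The retained weights are 0.20(1 - q), 0.70 x 0.95 = 0.665 and 0.10(1 - u), each divided by their sum.

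| q, u | Weights | Sum | Agitated / smooth / Riker 1-2 |
|---|---|---|---|
| 5%, 5% | 0.190, 0.665, 0.095 | 0.950 | 20.0% / 70.0% / 10.0% |
| 10%, 10% | 0.180, 0.665, 0.090 | 0.935 | 19.3% / 71.1% / 9.6% |
| 30%, 30% | 0.140, 0.665, 0.070 | 0.875 | 16.0% / 76.0% / 8.0% |
| 50%, 50% | 0.100, 0.665, 0.050 | 0.815 | 12.3% / 81.6% / 6.1% |
| 10%, 50% | 0.180, 0.665, 0.050 | 0.895 | 20.1% / 74.3% / 5.6% |

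The first row shows no bias, and the second a shift of about one percentage point in each class. In the last row the loss falls almost wholly on Riker 1-2, the class that the analysis does not define.

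**Step 5: direction for the correlation, also illustrative.** Take 20% agitated, a standard normal score, a logistic model giving a true correlation of -0.286, and intensive-care need of 5% after smooth and 30% after agitated emergence. If need does not otherwise depend on the score, the retained correlation is -0.261. If its log-odds also change with the score by between -1 and +1 per standard deviation, the retained correlation runs from -0.201 to -0.331 (numerical integration). It can therefore weaken or strengthen.

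**The case against.** The strongest reply is that the rule was never meant to be applied after surgery. It stands under eligibility, next to consent and after an entry rule for scheduled elective operations, and every patient attends a clinic where planned intensive care would be known. This stands as the more natural reading. It does not close the point, because the criterion's own words describe a postoperative need and nothing limits them.

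A second reply is that the rule may have a practical purpose: a patient taken straight to intensive care has no recovery-room series. That is plausible, though also an inference. It does not cover need arising after agents off, because recording has begun by then.

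A third reply is that the link from bad emergence to intensive care is undocumented and every rate is assumed. This stands in full, and the illustrations carry no weight in the conclusion.

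Three stronger readings are tempting, and the documents support none of them:

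- *The plan selects on the outcome.* No section says that the rule is applied after emergence begins.
- *The rule excludes everyone, because patients routinely go to a critical care unit.* The plan uses two different terms, and a reading that empties the study cannot be intended. This is a matter of wording.
- *The association is biased toward zero, or by a known amount.* Step 5 shows that the direction depends on an unknown.

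**Conclusion.** The point holds as an ambiguity with a conditional consequence. If the exclusion means care planned before surgery, there is little or no bias. If it is applied to need arising after agents off, it removes patients partly on the outcome, and severe emergence as a whole is under-counted provided that need is more common after bad emergence. The size of that under-count, and the size and direction of any effect on the correlations, cannot be determined from the documents.

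It is worth fixing because the rule defines the study population and a short amendment removes the possibility. Confidence is medium, since the benign reading is the likelier one.

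**What to change.** 1. Limit the exclusion to intensive care admission planned before surgery, and record this at the existing pre-anesthesia visit.
2. Keep consented patients whose need arises after agents off in the emergence analysis, using the Riker scores available.
3. Show Riker 1-2 as its own category. Otherwise unarousable patients who are retained have no place in the analysis.
4. Report the number of, and reasons for, any exclusions decided during surgery.
5. Reconcile the criterion with the routine discharge pathway by stating that the excluded unit differs from the neurosurgical critical care unit, if it does. This is a clarification, not a separate error.

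The cost is a short amendment to the eligibility and analysis text and one extra data field (need: none, planned, decided during surgery, arose after agents off; with reason). The downside is that some recovery-room series will be short and a third category will lie outside the smooth-versus-agitated contrast. These changes concern eligibility, analysis and reporting only; they imply no view on where patients should be cared for.

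### No reference blood pressure is designated and hemodynamics go to an unadjusted t-test, so this secondary comparison as planned does not separate an emergence rise from pre-existing pressure differences

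*Combined protocol and SAP*

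**What the plan says.** The Conclusion explains the interest in smooth emergence by stating that "blood pressure changes associated with violent emergence can cause intracranial hemorrhage and brain swelling". The hazard it names is a change in pressure.

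The Rationale and Data Collection sections give the same collection window. Data Collection reads: "Data will be collected from the time of turning off the anesthetic agents till the discharge from recovery room". The schedule follows: "Patients will be assessed every 5 minutes for the first 30 minutes and every 10 minutes for the next 60 minutes". The hemodynamic item on the data list is vital signs, in the run "Time of emergence from anesthesia, Vital signs, Glasgow Coma Scale (GCS) score". The list also holds items obtained before surgery (neuropsychological data, IQ, education, psychiatric history), but no preoperative, awake or intraoperative pressure or heart rate.

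The whole hemodynamic analysis is one sentence in Data Analysis: "Quantitative variables like hemodynamics will be analyzed using student's t-test". It does not name the groups, the time point, or whether levels or changes are tested.

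Standard perioperative management says that intraoperative monitoring of all patients includes "invasive and non-invasive blood pressure, temperature, urine output, depth of anesthesia (Entropy) and end tidal anesthetic agent concentration". It also says: "Preoperatively all patients will be seen by the anesthesiologists in the pre-anesthesia consult clinic". It describes separate points for stopping the inhalational agent and the remifentanil infusion.

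**The concern.** A change needs a starting value, and the plan does not name one. Read plainly, the t-test compares pressure levels after agents-off. The only emergence groups that the plan defines are smooth and agitated, and patients are not randomised to them. If the groups differed in pressure before emergence, for example because they differ in age, that difference would enter the comparison. A habitually hypertensive patient who wakes calmly would add a high value to the smooth group, and a normotensive patient with a large rise could look unremarkable.

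At stake is whether the hemodynamic result, which the plan would judge at p < 0.05, measures the quantity that the Conclusion calls dangerous. A second cost is flexibility: with no reference reading named in advance, its choice is left until after the data are seen.

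**Working it through.** **Inputs from the documents.** The collection window, the assessment schedule, the data list, the t-test sentence and the 0.05 threshold. No sample size, standard deviation, effect size or correlation is given, so there is no stated figure to reproduce. All sizes below rest on assumed values.

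**Step 1: is a pre-emergence reading available?** The schedule gives 30/5 = 6 readings, then 60/10 = 6, so 12 in all, or 13 if one is taken at the start. A time-0 reading is neither named nor excluded. When the window opens the patient is still anesthetized, since the inhalational agent is turned off from about 0.6 MAC. A reading at that moment would precede emergence, and pressure is already being monitored then. A reference is therefore obtainable; it is just not designated or used. Its timing is also loose, because the inhalational agent and remifentanil stop at separately described points.

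**Step 2: carry-over of a prior difference.** Assume equal variances before and at emergence, and a within-patient correlation r of 0.4 to 0.6. A group difference D in the reference reading then predicts r × D at emergence. With D = 10 mmHg (assumed):
- 0.4 × 10 = 4 mmHg
- 0.6 × 10 = 6 mmHg

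**Step 3: chance of a misleading significant result.** Suppose the groups have no difference in rise, and that a prior difference of d standard deviations reaches the emergence readings. For two equal groups of n, the two-sided normal approximation gives Φ(d/√(2/n) − 1.96) + Φ(−d/√(2/n) − 1.96). All n and d are assumed.

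| n per group | d = 0 | d = 0.25 | d = 0.5 | d = 0.8 |
|---|---|---|---|---|
| 15 | 5% | 10.5% | 27.8% | 59.1% |
| 25 | 5% | 14.3% | 42.4% | 80.7% |
| 50 | 5% | 24.0% | 70.5% | 97.9% |

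Here d is the part that reaches the emergence readings. If only a fraction r carries over as in Step 2, a prior difference of 0.5 SD with r = 0.5 belongs in the 0.25 column (0.5 × 0.5 = 0.25). For any d above zero, more patients make the error more likely.

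**Step 4: precision.** Relative to raw levels, the variance is 1 − r² after baseline adjustment and 2(1 − r) for a change score.
- r = 0.4: adjusted 1 − 0.16 = 0.84; change 1.2
- r = 0.6: adjusted 1 − 0.36 = 0.64; change 0.8

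Adjustment removes 16% to 36% of the variance. Interval widths shrink to √0.84 = 0.92 and √0.64 = 0.80 of their size, so by about 8% to 20%.

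**Step 5: what adjustment leaves behind.** If the 10 mmHg difference carries over only as r × 10, adjustment removes it, and a change score shows a spurious 4 − 10 = −6 to 6 − 10 = −4 mmHg. If it carries over in full, the change score shows nothing, and adjustment leaves 10 − 6 = 4 to 10 − 4 = 6 mmHg. In non-randomised groups neither method is right under both models. This is a reason to show the adjusted comparison and the observed rise together.

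**The case against.** A reader might infer that the design cannot separate an emergence rise from prior pressure. The documents do not support that. The window opens while the patient is still anesthetized, so a reading at its start could serve as a within-patient reference. Nor does the window sentence bar preoperative data, since the same section lists several preoperative items. What stands against the plan is that no such reading is specified. A reading at agents-off would also reflect anesthesia and not the patient's usual pressure.

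A reader might also take it as settled that raw levels will be compared. The sentence does not say so, and a t-test can be run on changes. Raw levels are the plain reading because no change, reference or covariate is mentioned, but this is an inference.

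It is tempting to say that an awake baseline already exists. The protocol says only that patients are seen in the clinic, not that pressure is recorded there. Only intraoperative pressure monitoring is explicit.

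Importance can be challenged too. Hemodynamics appear in neither the aim nor the hypothesis, which concern neuropsychological scores, limbic volumes and quality of emergence. The pressure hazard is one motivating sentence. This is correct and confines the point to a secondary comparison.

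Finally, the same analysis sentence leaves the groups unnamed and says nothing on how some 12 repeated readings are handled. A single covariate would not settle these gaps, so the fix below also covers time 0 and the repeated readings.

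**Conclusion.** The concern holds in limited form. The plan motivates smooth emergence by pressure change, designates no reference pressure, and sends hemodynamics to an unadjusted t-test. As planned, that comparison does not separate an emergence rise from prior differences between non-randomised groups. The defect is one of specification: a usable reference is within reach but is not defined or used.

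The size is unknown. The 4 to 6 mmHg carry-over, the 8% to 20% narrower intervals and the 10.5% to 97.9% chance of a misleading significant result (d from 0.25 to 0.8) all rest on assumed correlations, imbalances and group sizes. If the groups do not differ in pressure beforehand, the error rate stays at 5% and only precision is lost. The main neuropsychological question is not affected. The change is worth making because it is cheap and the plan commits to a significance test.

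**What to change.** 1. **Data list.** Add the last blood pressure and heart rate before the agents are turned off and, where recorded, the awake preoperative values.
2. **Time 0.** State which agent's stop starts the clock, as a data-collection definition only, with no change to care.
3. **Analysis.** Replace the raw t-test with a comparison of emergence hemodynamics between named groups, adjusted for the designated reference reading. Use ANCOVA at a stated time point or, to use the scheduled readings together, a repeated-measures model with baseline as covariate.
4. **Description.** Report the rise from the pre-agents-off reading by group, without a test.
5. **Limit.** Say in the plan that adjustment reduces baseline imbalance but cannot remove all confounding in non-randomised groups.

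The cost is a few values copied from the record and one covariate. The pre-agents-off reading comes from existing monitoring and needs no new measurement. The awake value is used only where it was recorded, so its completeness should be reported.

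### Patients who wake later get fewer and more widely spaced awake Riker scores, which can tie smooth/agitated class to time of emergence

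*Combined protocol and SAP*

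**What the plan says.** The Data Collection section sets the period: "Data will be collected from the time of turning off the anesthetic agents till the discharge from recovery room". The next sentence sets the schedule: "Patients will be assessed every 5 minutes for the first 30 minutes and every 10 minutes for the next 60 minutes". The Rationale repeats both. The schedule sentence names no starting point of its own. Agent turn-off is the only one offered nearby, and no assessment is listed after 90 minutes.

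Turn-off is itself two events under Standard perioperative management. First, "After the closure of scalp, inhalational agent will be turned off". Later, "Remifentanyl infusion will be turned off once the head is disengaged from head pins and after completion of the head dressing". The interval between them is not given.

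The Data Analysis section defines the outcome: "Emergence characteristics were classified as either smooth emergence (Riker scale 3-4) or agitated emergence (Riker scale >4". The two lowest levels of the scale, "2-very sedated, 1-unarousable", belong to neither class. No rule says which of a patient's repeated scores decides the class. The neuropsychological scores are then correlated with both the smooth/agitated class and the time of emergence. The opening summary says that very sedated patients are part of the spectrum seen after this surgery, but gives no frequency.

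**The concern.** If the clock starts at turn-off, the time a patient spends awake under scheduled observation is 90 minutes minus the waking time. The closely spaced checks also fall in the first 30 minutes, when a late waker is still at Riker 1-2. The opportunity to record agitation then depends on how fast the patient wakes.

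The study relates the same preoperative scores to both class and time of emergence. A neuropsychological score that predicts only slow waking could therefore also appear to predict the absence of agitation, and the two results would not be separate evidence. Scores never taken after 90 minutes cannot be recovered in the analysis.

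**Working it through.** The plan states no figure to reproduce, so the check counts assessments and illustrates the consequence.

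**Inputs from the documents**
- Schedule: 5, 10, 15, 20, 25, 30 minutes (6 checks), then 40, 50, 60, 70, 80, 90 minutes (6 checks), so 12 in all.
- Classes: smooth is Riker 3-4 and agitated is above 4.

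**Assumptions (not in the documents)**
- Time zero is agent turn-off.
- Waking is the first Riker score of 3 or more, at w = 10, 20 or 60 minutes.
- Any score above 4 makes the patient agitated.
- Each check after waking carries the same independent risk p of a score above 4, for every patient.

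**Formula.** Let k be the number of scheduled checks later than w. Then P(classed agitated) = 1 - (1 - p)^k.

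| Waking at | k | p = 10% | p = 5% |
|---|---|---|---|
| 10 min | 10 | 1 - 0.9^10 = 65% | 1 - 0.95^10 = 40% |
| 20 min | 8 | 1 - 0.9^8 = 57% | 1 - 0.95^8 = 34% |
| 60 min | 3 | 1 - 0.9^3 = 27% | 1 - 0.95^3 = 14% |

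**Counting convention.** If a check falling exactly at waking is included, k becomes 11, 9 and 4. At p = 10% the chances are 69%, 61% and 34%, the same pattern.

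**Later time zero.** If the clock started 20 minutes after turn-off (assumed), the checks at or after waking would number 12 for waking at 10 minutes and 6 for waking at 60. At p = 10% that is 1 - 0.9^12 = 72% against 1 - 0.9^6 = 47%. The gap shrinks but remains.

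**Different course of agitation.** Suppose instead that there is one episode of length d, starting at waking, with waking at a random point in a gap of s minutes between checks. It is caught with probability min(1, d/s).
- d = 2 minutes: 2/5 = 40% on the 5-minute grid, 2/10 = 20% on the 10-minute grid.
- d = 5 minutes: 100% against 5/10 = 50%.
- d = 8 minutes: 100% against 8/10 = 80%.
- d = 10 minutes or more: 100% on both, for waking up to 80 minutes.

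Under this second model the dependence on waking time comes only from the wider spacing, and it disappears for longer episodes.

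**The case against.** A reader might infer that slow wakers tend to be classed as smooth. The documents do not support that as it stands, for four reasons.

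- It needs a rule that any score above 4 sets the class, and the plan states none. Under a first-awake-score or last-score rule, the number of checks does not drive the class. Timing still might: with the last score at 90 minutes, a patient who woke at 10 minutes is judged 80 minutes after waking, and one who woke at 75 minutes is judged 15 minutes after.
- The slowest wakers are not smooth. Patients still at Riker 1-2 at 90 minutes fall in neither class.
- The 60-minute waking time is an illustration. The documents give no emergence times, and between 10 and 20 minutes the gap is only 65% against 57%. A constant independent risk is also an assumption, and the episode model shows that the gap can be nil.
- The mismatch with discharge matters only if recovery-room stays run past 90 minutes from time zero, and no length of stay is given. The collection sentence promises data until discharge, not Riker scores at any particular spacing.

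It can also be objected that agitation may precede waking, since the Background describes uncoordinated movement before patients respond to commands, and time of emergence is not defined. Defining waking as the first Riker score of 3 or more meets this for the count of checks, because a score above 4 is then itself awake. How strongly class is tied to time of emergence still depends on how that time is defined.

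All four reservations stand as limits on direction and size. They do not remove the basic fact that, with a clock fixed at turn-off, later waking leaves fewer and sparser awake scores.

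**Conclusion.** The point holds in conditional form. The schedule ends at 90 minutes while collection continues to discharge, and if timed from turn-off it observes late wakers less. If any score above 4 sets the class, late wakers are less likely to be recorded as agitated at equal risk, and class becomes partly tied by the schedule to the other analysed outcome. Patients not awake by 90 minutes have no class.

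The size cannot be fixed from the documents. Under the assumed 10% independent risk, the difference is 65% against 57% for waking at 10 and 20 minutes, and 65% against 27% for 10 and 60 minutes. It may be zero if agitation begins at waking and lasts at least 10 minutes. The change is worth making because it is cheap and the missing scores cannot be reconstructed later.

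**What to change.** In Data Collection:
- State time zero, naming which turn-off starts the clock.
- Record the time of the first Riker score of 3 or more for each patient.
- Restart the grid (5-minute checks, then 10-minute checks) at that time, and continue scoring to recovery-room discharge. Patients not yet at Riker 3 also continue to be scored past 90 minutes.

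In Data Analysis:
- Set the smooth/agitated class from a pre-specified window counted from the first Riker score of 3 or more, with a stated rule for which score decides.
- Report separately patients discharged before the window closes and patients who never reach Riker 3.

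Restarting the grid matters. A 60-minute window from waking on the existing turn-off grid, continued every 10 minutes, would still give 8 checks for waking at 10 minutes (15, 20, 25, 30, 40, 50, 60, 70) and 6 for waking at 60 (70 to 120). That is 57% against 47% at p = 10%. With the grid restarted, the same window gives every fully observed patient 6 + 3 = 9 later checks. The 60 minutes is only an example; the investigators should choose the window.

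The cost is wording in two sections, plus extra scores and longer observation in late wakers. For a patient waking at 60 minutes, the example means 9 later checks instead of 3.
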